7.1.1. Dose-Limiting Toxicity

No dose-limiting toxicities have been identified to date in humans receiving a single dose of rFVIII Fc up to 65 IU/kg. Also, no dose-limiting toxicities were observed in the preclinical animal studies where repeat doses of up to 1000 IU/kg were evaluated.

Doses higher than 65 IU/kg may be used in this study, such as in surgery, to achieve the required FVIII levels to prevent bleeding. However, the maximum dose during surgery will not exceed the predicted accumulated C_{max} of approximately 200% of normal (normal ranges are 50-150% FVIII activity). In pediatric subjects, dose adjustments up to a maximum prophylactic dose of 80 IU/kg and frequency of administration up to every 2 days can be used if necessary to maintain adequate FVIII activity trough levels and prevent spontaneous bleeding events.

An overdose of rFVIII Fc is defined as any single prophylactic dose >100 IU/kg (see Section 15.4.1).

7.1.2. Inhibitor Testing

If inhibitor development is suspected at any time during the study (for example, the expected plasma FVIII activity levels are not attained, or if bleeding is not controlled as expected following dosing), inhibitor testing will be performed by the central laboratory. The definition of a positive result for inhibitor is any inhibitor (≥ 0.6 BU/mL) identified and confirmed on 2 separate samples drawn approximately 2 to 4 weeks apart. Both tests must be performed by the central laboratory using the Nijmegen-modified Bethesda assay.

A high-titer inhibitor is defined as ≥ 5.00 BU/mL identified and confirmed on 2 separate samples drawn approximately 2 to 4 weeks apart. Both tests must be performed by the central laboratory using the Nijmegen-modified Bethesda assay.

When an inhibitor test is performed at the local laboratory, an aliquot of the sample must be sent in parallel to the central laboratory.

For FVIII inhibitor testing, a wash out of at least 48 hours is recommended.

For subjects who have fewer than 50 exposure days (EDs) with rFVIII Fc following completion of Visit 1, a visit may be conducted to perform inhibitor testing at the time subjects reach 10-15 EDs, 50-75 EDs, and 100-125 EDs, as applicable. If the timing does not coincide with a scheduled visit, an unscheduled visit may be conducted.

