16.7.2. Methods of Analysis

The proportion of subjects with inhibitors during rFVIII Fc administration will be provided with the exact (Clopper-Pearson) 2-sided, 95% confidence interval. Any subject with an inhibitor following the initial rFVIII Fc administration will be counted in the numerator; however, only subjects who have completed at least 50 EDs and 100 EDs from their initial rFVIII Fc administration will be included in the denominator. Unless all subjects complete at least 50 EDs, the proportion of subjects with inhibitors will also be calculated using all subjects, regardless of the amount of exposure to rFVIII Fc, in the denominator.

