8.3.2. Inhibitor Development

Inhibitor results of the Nijmegen-modified Bethesda Assay from the central lab will be listed. Results from blood samples collected during surgical/rehabilitation periods for the purpose of determining the presence of an inhibitor will be included.

A positive inhibitor occurs where a subject has a value ≥ 0.6 Bethesda Units (BU/mL) confirmed on re-testing between 2 and 4 weeks later. Both tests must be performed by the central laboratory.

A “low” titer inhibitor occurs where a subject has a value between 0.6 and <5.0 Bethesda Units (BU/mL) confirmed on re-testing between 2 and 4 weeks later.

A “high” titer inhibitor occurs where a subject has a value ≥ 5.0 Bethesda Units (BU/mL) confirmed on re-testing within 2 to 4 weeks.

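### The 50-ED and 100-ED denominators for the primary inhibitor proportion need exposure but no inhibitor test, so a subject with no result at or after the milestone counts as inhibitor-free

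*Protocol*

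**What the plan says.** **Numerator and denominator.** Protocol 16.7.2 gives the numerator as "Any subject with an inhibitor following the initial rFVIII Fc administration will be counted in the numerator". For the denominator, "only subjects who have completed at least 50 EDs and 100 EDs from their initial rFVIII Fc administration will be included in the denominator". I read this as two separate denominators, one for each milestone. If not everyone reaches 50 EDs, a further proportion uses all subjects whatever their exposure. None of these denominators mentions an inhibitor test.

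**What counts as positive.** Protocol 7.1.2 and SAP 8.3.2 ("A positive inhibitor occurs where a subject has a value" of at least 0.6 BU/mL, confirmed 2 to 4 weeks later) both need two central-laboratory results. A subject who is not tested cannot become a case.

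**When testing happens.** Protocol 7.1.2 words milestone testing as a permission: "a visit may be conducted to perform inhibitor testing". It names three windows (10 to 15, 50 to 75 and 100 to 125 EDs) and limits them to subjects whose rFVIIIFc exposure after Visit 1 is below 50 EDs. The fallback is permissive too: "If the timing does not coincide with a scheduled visit, an unscheduled visit may be conducted". Protocol 7.1 sets visits every 6 months, plus or minus 2 weeks. Protocol 14.2 lists the inhibitor assay as a laboratory safety test and leaves its timing to Section 4.

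**SAP.** Sections 8.1 and 8.3.2 plan a listing of inhibitor results, with no proportion, denominator or interval. Section 5.1.3 has no rule for a missing inhibitor test.

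**The concern.** A denominator for a laboratory-defined event should hold subjects in whom the event could have been seen. Here the entry condition is exposure. A subject who reaches his 50th or 100th ED and then leaves, misses a visit or gives an invalid sample is scored as a non-event at that milestone, although nothing was measured there. Each such subject can only lower the proportion and narrow the interval.

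A second mismatch works the other way. Someone whose inhibitor appears before the milestone and who stops treatment stays in the numerator but never enters the denominator. This is a realistic path, because Protocol 11.1 requires discontinuation for a high-titer inhibitor. The numerator is then not a subset of the denominator, as the Clopper-Pearson interval assumes.

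The SAP is stricter elsewhere. Antibody percentages (8.3.3) need a post-baseline evaluation for the time point or interval in question, and laboratory-abnormality percentages (8.3.1.3) need at least one post-baseline value. The primary endpoint has the looser rule.

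**Working it through.** **Planned numbers.** Protocol 16.10: 144 + 50 = 194. SAP 3.3.1: 144 + 50 + 12 + 8 = 214. Both match the stated totals. The study is descriptive, so there is no power or precision calculation to reproduce. These are planned enrolments and serve only as upper bounds for the number reaching 50 or 100 EDs.

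**Room for an untested subject.** Six months is about 182.6 days. Dosing every 3 days gives 182.6 / 3 = 61 EDs between visits; every 5 days gives 182.6 / 5 = 37. A subject can therefore pass a milestone well before his next scheduled visit. To remain untested he must leave or miss that visit and also have no final-visit result.

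**Effect of requiring a test, no inhibitors observed.** The exact two-sided 95% upper limit for 0 of n is 1 − 0.025^(1/n). The untested share is not in the documents, so the shares below are assumptions.

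| Assumed share without a later test | n from 194 | Upper limit | n from 50 (pediatric) | Upper limit |
|---|---|---|---|---|
| 0% (rule as written) | 194 | 1.88% | 50 | 7.11% |
| 10% | 175 | 2.09% | 45 | 7.87% |
| 20% | 155 | 2.35% | 40 | 8.81% |
| 30% | 136 | 2.68% | 35 | 10.0% |

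For the SAP total, 10% untested moves the limit from 1.71% (n = 214) to 1.89% (n = 193).

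**One inhibitor observed.** As written, 1/194 = 0.52%, upper limit 2.84%. With 20% untested, 1/155 = 0.65%, upper limit 3.54%.

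**Early-case mismatch.** Suppose one of 194 subjects has an inhibitor before 50 EDs and stops, and the other 193 pass 50 EDs. As written, 1/193 = 0.518%; with the case in both places, 1/194 = 0.515%. For 50 pediatric subjects, 1/49 = 2.04% against 1/50 = 2.00%. The shift is small and opposite in direction to the effect of untested subjects.

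**The case against.** The strongest reply is that hardly anyone will lack a later result.

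- The permissive wording covers only subjects with fewer than 50 EDs after Visit 1, and those visits supplement the six-monthly schedule.
- Several places point to routine testing. Protocol 14.2 lists the assay among tests to be performed. Protocol 7.1 asks prophylaxis subjects to time clinic visits so that inhibitor testing is accurate. Protocol 11.2 gives withdrawn subjects a final visit per Table 1. Protocol 7.1.2 requires central testing whenever an inhibitor is suspected.
- EDs count from the first rFVIIIFc dose, parent-study data are integrated (Protocol 16), and follow-up can last up to 4 years. The pediatric parent study aims for at least 50 EDs (Protocol 5.1.3), so some subjects may already have a result beyond 50 EDs.
- The all-subject proportion already places early cases in both numerator and denominator.
- SAP 5.2.2 bases percentages on non-missing data by default.

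Most of this stands, and it limits the size of the effect. A reader might infer from the word "may" that inhibitor testing in general is optional, or that untested subjects are common. The documents support neither reading. The grid of Table 1 is missing from the text available for this review, so routine and final-visit testing cannot be confirmed in detail, and its absence from that text is not an omission from the plan.

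The reply does not supply a rule. Missed visits, losses and invalid samples occur under any schedule, and 16.7.2 does not say how to count those subjects. The all-subject proportion needs no test either. The SAP default does not help, because no inhibitor percentage is planned there and a result from before the milestone could satisfy it.

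**Conclusion.** The point holds as a gap in the denominator definition, and it is minor. Under Protocol 16.7.2 a subject with no central-laboratory result at or after the milestone, and no earlier confirmed inhibitor, counts as inhibitor-free. An early case who never reaches the milestone is in the numerator only.

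The size cannot be derived from the documents. With no events and 10% untested (assumed), the upper limit moves by 2.09 − 1.88 = 0.21 percentage points for 194 subjects, and by 7.87 − 7.11 = 0.76 points for 50 pediatric subjects. Both treat planned enrolment as the number reaching the milestone.

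A reader might infer that the reported proportion is known to be biased downward. That goes too far. With no events the estimate is zero under either rule, and the early-case mismatch pushes the other way, so the documents do not fix the net direction.

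**What to change.** In Protocol 16.7.2, state that there are two denominators. A subject enters the 50-ED (100-ED) denominator only if he has a valid central-laboratory inhibitor result at or after his 50th (100th) ED, counting parent-study and extension results from the first rFVIIIFc dose, or has a confirmed inhibitor earlier. Report, for each milestone, how many subjects reached the exposure but were excluded for lack of a test. The clause on earlier inhibitors also places every case in both numerator and denominator.

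Carry the proportion, this denominator rule and the Clopper-Pearson interval into SAP 8.1 and 8.3.2. This adds an analysis to the SAP, since those sections have no denominator to reword. SAP Section 1 limits the analysis to 8HA01EXT data and SAP 7.3.2 counts EDs within the extension, so the SAP must also say that parent-study EDs and inhibitor results are used here.

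The cost is a protocol clarification, one added SAP table, slightly smaller denominators and a slightly wider interval. No visits or blood samples are added. If nearly everyone was tested, the result barely changes and the reported count shows it.

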7.1.3. Anti-rFVIII Fc Antibody Testing

In order to characterize non-neutralizing antibodies that may react with rFVIII Fc, an exploratory assay that differentiates between antibodies with specificities for rFVIII Fc, full-length FVIII (Advate®), or Fc will be used to test for the presence of anti-drug antibody in study subjects.

CONFIDENTIAL

The information contained herein may not be used, disclosed, or published without the written consent of Biogen Idec MA Inc.

The electrochemiluminescent assay (ECLA) used for this test is approximately 10-to 20-fold more sensitive than the Nijmegen-modified Bethesda assay. A blood sample will be stored for future testing of anti-rFVIII Fc antibody at the same time points that samples are drawn for inhibitor testing, or for any clinical event deemed relevant to anti-rFVIII Fc testing (see [Table 1](#) and [Table 2](#)).

7.1.4. Bleeding Episodes

If a subject experiences a bleeding event at any time during study treatment, he or his caregiver should follow the guidance for treatment of bleeds, a document to be provided to each subject and/or caregiver. Guidance for study staff is provided in [Appendix A](#). The type of bleed and each injection and injection dose required to stop the episode will be recorded in the subject's electronic patient diary (eDiary).

In this study, when a subject reports a bleed or hemorrhage, and is treated with study drug, it will be classified as spontaneous or traumatic by the subject. The subject's eDiary will serve as the source document for bleeding episodes while on study.

In this study, a bleed will be defined as follows: a bleeding episode starts from the first sign of a bleed and ends no more than 72 hours after the last treatment for the bleed, within which any symptoms of bleeding at the same location, or injections less than or equal to 72 hours apart, are considered the same bleed. Any injection to treat the bleed, taken more than 72 hours after the preceding one, will be considered the first injection to treat a new bleed at the same location. Any bleeding at a different location is considered a separate bleed regardless of time from last injection.

Spontaneous bleeding episodes: Bleeding episodes should be classified as spontaneous if a subject records a bleeding event when there is no known contributing factor such as definite trauma or antecedent strenuous activity. The determination of "strenuous" is at the discretion of the Investigator. Both spontaneous bleeding episodes (the occurrence of hemorrhage where neither the subject nor a caregiver can identify a reason) and traumatic bleeding episodes (hemorrhage occurring secondary to an event such as trauma or strenuous activity) will be collected. Target joints can have spontaneous bleeding episodes.

Traumatic bleeding episodes: Bleeding episodes should be classified as traumatic if a subject records a bleeding event when there is a known or believed reason for the bleed. For example, if a subject were to exercise strenuously and then have a bleed in the absence of any obvious injury, the bleed would still be recorded as a traumatic bleed. Target joint bleeding episodes can be traumatic if a known action led to bleeding into the joint.

7.1.4.1. Information to be Recorded

The incidence of bleeding in this study will be obtained from eDiaries and any medical records while the subject is receiving study treatment. The subject/subject's caregiver should enter eDiary information in a timely manner to facilitate appropriate medical review and dosing guidance. The clinical sites and monitors will ensure that there is consistency between the subject's eDiary record and eCRFs. During the clinical visits and telephone calls with the subject/subject's caregiver, the Investigator will verify whether or not a bleed has occurred, and

CONFIDENTIAL

The information contained herein may not be used, disclosed, or published without the written consent of
Biogen Idec MA Inc.

if any bleed was “spontaneous” or “traumatic.” If, following this discussion, the Investigator judges that the subject’s/subject’s caregiver classification was incorrect, the Investigator will document it in (a) the subject’s medical notes with the rationale for the new classification, and (b) the eCRF, documenting the new classification of the bleed according to the Investigator, and whether or not the subject’s caregiver agreed with this new classification. With regard to dose changes, the Investigator’s classification of “spontaneous” or “traumatic” will be used (if different from the classification recorded in the eDiary by the subject/subject’s caregiver).

Bleeding episodes will not be reported as AEs; however, the concomitant events associated with a bleed may be reported as an AE if appropriate (i.e., a fracture in an elbow). Both spontaneous bleeding episodes and traumatic bleeding episodes will be collected.

The following information will also be documented in the eDiary:

- The type of bleeding episode (e.g., spontaneous, traumatic, or related to increased physical activity).
- The date the bleeding event occurred.
- The dose administered for the bleeding episode, including any repeat doses.
- The location of the bleed (joint, internal, skin/mucosa, or muscle).
- The reason for administering the dose (medical or nonmedical reasons [e.g., strenuous activity or other reason])

7.1.4.2. Procedure to Treat the Bleeding Episode

The dose of rFVIII Fc to treat the bleeding episode will be based on the subject’s clinical condition, known PK information from the previous study or FVIII trough/peak (recovery) measurements in this study, type and severity of the bleeding event (see [Appendix A](#) for guidance on dosing), and input from the Sponsor, if necessary.

Subjects and subjects’ caregivers should be instructed to treat at the first sign of a bleeding episode with a single dose of rFVIII Fc. Most bleeding episodes should resolve with a single dose of rFVIII Fc. If a subject has one spontaneous bleed and the Investigator is concerned the trough level is too low, the Investigator should contact the Sponsor to discuss next steps for this subject.

- **If the bleeding episode stops with a single IV dose of rFVIII Fc**, the subject should return to his previous dosing regimen and will be treated with his next dose of rFVIII Fc as previously scheduled, even if this results in consecutive daily doses.
- **If the bleeding episode does not stop within 24 hours with the single IV dose of rFVIII Fc**, the subject or the subject’s caregiver should consult with the Investigator for an optimal rFVIII Fc dose and dosing interval, and should administer a second dose (first follow-up dose) no less than 24 hours after the initial dose. Administration of the second dose of rFVIII Fc as follow-up treatment will be determined by the Investigator based on the subject’s clinical condition. Please refer to [Appendix A](#) for rFVIII Fc dosing guidance. Once the bleeding event stops, the subject will return to his previous dosing

CONFIDENTIAL

The information contained herein may not be used, disclosed, or published without the written consent of
Biogen Idec MA Inc.

regimen and will be treated with his next dose of rFVIII Fc as previously scheduled, even if this results in consecutive daily doses.

- **If the bleeding event does not stop with 2 doses (initial and follow-up treatments) of rFVIII Fc**, the subject or the subject's caregiver should contact the Investigator for advice. Following consultation with the Investigator, a third dose of rFVIII Fc will be administered 24 hours after the administration of the second dose of rFVIII Fc. The third dose (second follow-up dose) may be at the same dose as the second dose or a dose determined by the Investigator based on the subject's clinical condition. Please refer to [Appendix A](#) for rFVIII Fc dosing guidance. Once the bleeding event resolves, the subject will return to his previous dosing regimen and will be treated with his next dose of rFVIII Fc as previously scheduled, even if this results in consecutive daily doses.

If the bleeding event still has not stopped after 3 doses (initial and 2 follow-up doses) of rFVIII Fc, the Investigator should contact the Sponsor Medical Monitor to discuss the next steps for treatment of the subject.

7.1.4.3. Dose and/or Interval Modification Following Bleeding Episodes

Dose and/or interval modification following bleeding episodes can occur if a subject experiences ≥ 2 moderate or major spontaneous bleeding episodes over a rolling 8-week period. The Investigator can adjust the rFVIII Fc dose as follows:

- If an increase is required, the dose may be increased in increments of at least 5 IU/kg.
- The dose and/or interval may be adjusted after discussion with the Sponsor Medical Monitor.
- See Section [5.3](#) for description of regimen changes.

7.2. Overall Study Duration and Follow-Up

The study period will consist of Screening and Treatment.

Subjects first dosed with rFVIII Fc when < 12 years of age will be followed to at least 100 EDs, even if rFVIII Fc becomes commercially available.

All subjects will have the opportunity to participate in this study for up to 4 years or until rFVIII Fc is commercially available in the applicable participating country.

7.2.1. Screening

Subject eligibility for the study will be determined prior to enrollment (Visit 1). The EOT Visit for the preceding study may act as Visit 1 for this study, however, if there is a gap of > 37 days following the EOT Visit of the preceding study, all laboratory assessments for Visit 1 must be performed and eligibility confirmed prior to dosing with rFVIII Fc.

Informed consent for the extension study may be reviewed and obtained during the EOT Visit of the previous study, and if not then consent must be obtained at Visit 1.

CONFIDENTIAL

The information contained herein may not be used, disclosed, or published without the written consent of Biogen Idec MA Inc.

7.2.2. Treatment

Eligible subjects will self-administer rFVIII Fc according to their assigned treatment regimen. Caregivers or Sponsor-approved designees may also administer rFVIII Fc. Where appropriate, rFVIII Fc may be administered in the clinic.

7.2.3. Follow-Up

A final study visit will be conducted approximately 147 (+7) days after the last dose of rFVIII Fc. This 7 day follow-up visit is not required if a subject ends his participation in the extension study to enroll into another rFVIII Fc study.

7.3. Study Stopping Rules

The Sponsor may terminate this study at any time, after informing Investigators. Investigators will be notified by the Sponsor or designee if the study is placed on hold, completed, or closed.

The study must be stopped in the following cases:

- Three subjects develop high titer (i.e. ≥ 5.00 BU/mL) inhibitor, as defined in Section 7.1.2. This number can be adjusted based on sample size when more subjects might be included into this trial from other rFVIII Fc studies.
- An unexpected, serious, or unacceptable risk to the study subjects.

If the study is stopped, the events will be investigated, enrollment will be stopped, and current subjects will stop dosing with rFVIII Fc. If, in consultation with the Sponsor's Safety Surveillance Team, it is determined that the study should be permanently discontinued, then subjects will attend a final visit.

7.4. End of Study

The end of study is last subject, last visit.

CONFIDENTIAL

The information contained herein may not be used, disclosed, or published without the written consent of Biogen Idec MA Inc.

8. SELECTION OF SUBJECTS

8.1. Inclusion Criteria

To be eligible to participate in this study, candidates must meet the following eligibility criteria at the time of signing the informed consent at Visit 1 of the study, or at the EOT of the previous study:

1. Ability to understand the purpose and risks of the study and provide signed and dated informed consent and authorization to use protected health information (PHI) in accordance with national and local subject privacy regulations. Parental or guardian consent is required for subjects who are less than 18 years of age or unable to give consent, or as applicable per local laws. Subjects who are less than 18 years of age may provide assent in addition to the parental/guardian consent, if appropriate.
2. Subjects who have completed the studies 997HA301, 8HA02PED, or other studies with rFVIII Fc.

